### 16.1.1. **Solicited Adverse Events**

Solicited administration site events and solicited systemic events to be summarized are included in Table H. Intensity scales for solicited events (administration site and systemic) are included in [Table I](#) and [Table J](#).

**Table H:      Solicited events**

Solicited administration site events	Solicited systemic events
Pain at Injection Site	Fever
Erythema / Redness at Injection Site	Headache
Swelling at Injection Site	Fatigue Myalgia Arthralgia Shivering/Chills Gastrointestinal symptoms (nausea, vomiting, diarrhea and/or abdominal pain)

**Table I:      Intensity scales for solicited events – pain, headache, fatigue, myalgia, arthralgia, shivering/chills and gastrointestinal symptoms**

Event	Intensity grade	Parameter
Pain at administration site	0	None
	1	Mild: Any pain neither interfering with nor preventing normal everyday activities.
	2	Moderate: Painful when limb is moved and interferes with everyday activities.
	3	Severe: Significant pain at rest. Prevents normal everyday activities.
Headache	0	None
	1	Mild: Headache that is easily tolerated

Event	Intensity grade	Parameter
	2	Moderate: Headache that interferes with normal activity
	3	Severe: Headache that prevents normal activity
Fatigue	0	None
	1	Mild: Fatigue that is easily tolerated
	2	Moderate: Fatigue that interferes with normal activity
	3	Severe: Fatigue that prevents normal activity
Myalgia	0	None
	1	Mild: Myalgia that is easily tolerated
	2	Moderate: Myalgia that interferes with normal activity
	3	Severe: Myalgia that prevents normal activity
Arthralgia	0	None
	1	Mild: Arthralgia that is easily tolerated
	2	Moderate: Arthralgia that interferes with normal activity
	3	Severe: Arthralgia that prevents normal activity
Shivering/Chills	0	None
	1	Mild: Shivering that is easily tolerated
	2	Moderate: Shivering that interferes with normal activity
	3	Severe: Shivering that prevents normal activity
Gastrointestinal symptoms	0	None
	1	Mild: Gastrointestinal symptom that is easily tolerated
	2	Moderate: Gastrointestinal symptom that interferes with normal activity
	3	Severe: Gastrointestinal symptom that prevents normal activity

**Table J: Intensity scales for solicited events – erythema/swelling and fever**

	Erythema/swelling	Fever
0:	≤20 mm	<38.0 °C <100.4 °F
1:	> 20 - ≤50 mm	≥38.0 °C (100.4 °F) - ≤38.5 °C (101.3 °F)
2:	> 50 - ≤100 mm	>38.5 °C (101.3 °F) - ≤39.0 °C (102.2 °F)
3:	>100 mm	>39.0 °C (102.2 °F)

**Table K: Solicited events lower level term codes and decodes**

Solicited event	Lower level term code	Corresponding Lower level term decode
Pain	10022086	Injection site pain
Erythema	10022061	Injection site erythema
Swelling	10053425	Injection site swelling
Fever	10016558	Fever
Headache	10019211	Headache
Fatigue	10016256	Fatigue
Myalgia	10028411	Myalgia
Arthralgia	10003239	Arthralgia
Shivering/Chills	10008531	Chills
Diarrhoea	10012735	Diarrhoea
Abdominal pain	10000081	Abdominal pain
Nausea	10028813	Nausea
Vomiting	10047700	Vomiting

Solicited events will be summarized and listed as:

- The number and percentage of participants with at least one administration site event (solicited only), with at least one systemic event (solicited only) and with any solicited event during 4-day follow-up and 7-day follow-

CCI

up period after vaccination, and also events ongoing at the end of the 7 day follow up period, will be tabulated with exact 95% CI by visit. These summaries will be repeated by age group.

- The number and percentage of participants, with exact 95% CIs, reporting each solicited events (administration site and/or systemic) will be summarized separately for all grades, Grade 3 and medically attended events during the 4-day follow-up and the 7-day follow-up period (i.e., the day of vaccination and 6 subsequent days), following each dose and overall dose and overall participant. This summary will be repeated by age group.
- The number and percentage of participants, with exact 95% CIs, reporting administration site solicited events will be summarized separately for all grades, Grade 3 and medically attended events during the 4-day follow-up and the 7-day follow-up period (i.e., the day of vaccination and 6 subsequent days), following each dose, overall dose and overall participant. This summary will be repeated by age group.
- The number and percentage of participants, with exact 95% CIs, reporting systemic solicited events will be summarized separately for all grades, Grade 3 and medically attended events during the 4-day follow-up and the 7-day follow-up period (i.e., the day of vaccination and 6 subsequent days), following each visit and overall visits and overall participant. This summary will be repeated by age group.
- Duration in days of solicited events will be summarized as follows:
  - Duration (days) of solicited administration site events will be summarized following each dose and overall,
  - Duration (days) of solicited systemic events will be summarized following each visit and overall,
  - where duration for the above solicited events summaries is defined as:
    - Duration = (End date – Start date) + 1, for AEs with Grade > 0
      - If a solicited AE is still Grade > 0 at Day 30, the end date will be considered equal to vaccination date + 29 days.
- Number of days with Grade 3 solicited events will be summarized as follows:
  - Number of days with Grade 3 solicited administration site events will be summarized following each dose and overall,
  - Number of days with Grade 3 solicited systemic events will be summarized following each visit and overall,
  - where number of days with Grade 3 events is derived as the sum of all post-vaccine days with known Grade 3 for the events category (administration site events or systemic events), recorded up to Day 30 post-vaccine.
- For fever, the number and percentage of participants reporting fever by half degree (°C) cumulative increments in applicable systemic event summaries.
- The percentage of participants with each solicited administration site event and solicited systemic event (any grade and Grade 3) will be represented graphically for each group after each dose, during the 4-day and 7-day follow-up period.
- All solicited administration site events will be included in a listing.
- All solicited systemic events will be included in a listing.

- Sensitivity analysis will be performed to present differences in severity/intensity scales between participant and principal investigator assessments for solicited events: erythema, swelling and fever. All summaries and listings aside from this sensitivity analysis are based on the participant assessments – only the sensitivity outputs will be based on the investigator assessment. This will be summarized separately for the solicited administration site events (erythema and swelling) and for the solicited systemic event (fever). The differences between participant and principal investigator assessments will be included in a listing.
- Subgroup analysis will be created for the solicited administration site events and the solicited systemic events within 7 days of each dose split by age category, race, ethnicity and gender.

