## 6.5. Statistical Tests

The default significant level will be (5%), CIs will be 95% and all tests will be two-sided, unless otherwise specified in the description of the analyses.

95% CI for proportion will be based on exact Clopper-Pearson CI [18].

95% CI for group difference in proportion will be based on Miettinen and Nurminen CI [18].

The least square point estimate and its 2-sided 95% CI will be derived from an ANCOVA model on log10 transformed concentration/titer. Covariate and factor included in the model are described in [7.1](#).

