## **12. PRIOR, CONCOMITANT AND CO-ADMINISTERED VACCINATIONS**

[figure not shown]
Prior, concomitant and co-administered vaccination will be coded with the current version of the World Health Organization Drug Dictionary (WHODD).

Prior vaccinations are vaccinations per protocol given to participants prior to the dosing of study intervention and are recorded on the eCRF.

Concomitant vaccinations are defined as any vaccine that the participant is receiving as of the time of enrolment or receives during the study (other than study interventions) as recorded on the “Concomitant Vaccination” page of the eCRF.

The number and percentage of participants and doses with concomitant vaccination during the 30-day follow-up period (i.e., on the day of vaccination and 29 subsequent days) will be summarized by group after each vaccine dose

CCI

and overall, with exact 95% CIs.

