## 13. MEDICATIONS

The number and percentage of participants and doses using concomitant medication (any medication, any medical device, any antipyretic and any antipyretic taken prophylactically, respectively) during the 7-day follow-up period (i.e., on the day of last study intervention and 6 subsequent days) and during the 30-day follow-up period (i.e., on the day of last study intervention and 29 subsequent days), will be summarized by study intervention group for each study intervention administration and overall with exact 95% CIs for the ES. Concomitant medications will also be presented in listings.

See [APPENDIX 2](#) for handling of partial dates for medications, in the case where it is not possible to define a medication as prior or concomitant, the medication will be classified by the worst case, i.e., concomitant.

- ‘Prior’ medications are medications which started prior to the dose of study intervention.
- ‘Concomitant’ medications are medications which started on or after the day of the administration of study intervention.

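### Exact binomial confidence intervals on the pooled dose and visit rows ignore repeated observations within a participant; the pooled denominators need defining, and those intervals need adjusting or dropping

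*SAP*

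**What the plan says.** SAP 6.5 states the rule without exception: "95% CI for proportion will be based on exact Clopper-Pearson CI". It sets the level at 95%.

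Four places apply exact 95% intervals to a unit other than the participant, or appear to:

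- SAP 16.1.1, each solicited event and administration site events: the seven-day window and the rows wanted ("i.e., the day of vaccination and 6 subsequent days), following each dose and overall dose and overall participant"), with near-identical wording for site events.
- SAP 16.1.1, systemic events: rows "following each visit and overall visits and overall participant".
- SAP 12: "The number and percentage of participants and doses with concomitant vaccination during the 30-day follow-up period".
- SAP 13: "The number and percentage of participants and doses using concomitant medication".

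SAP 12 and 13 name doses as a unit outright. SAP 16.1.1 does not define its pooled denominators, and its sentences open with the percentage of participants. A dose or visit denominator there is an inference, but a strong one: a participant-level overall row is listed separately and would otherwise duplicate the pooled row.

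SAP Table B gives three injections per participant in each arm. Co-Ad receives them at two vaccination visits and Control at three. SAP 16.1 adds that a site event recorded after co-administered injections counts as one occurrence. It does not say whether the denominator is also reduced. Neither document provides a clustered interval or a caveat for pooled rows.

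**The concern.** Clopper-Pearson has its guaranteed coverage only for independent trials. A participant who reacts to, or takes an antipyretic after, one vaccination is more likely to do so after the next. Pooling doses or visits then presents about 265 people as 530 or 795 independent observations, and the printed interval claims more precision than the data hold.

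SAP 16 plans no between-group comparison for safety, so readers will compare the printed intervals by eye. The pooled rows would carry the narrowest intervals in these tables under the label of an exact 95% interval. For systemic events pooled over visits, the understatement would be larger in Control than in Co-Ad.

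**Working it through.** **Plan's own figure.** The documents state no width, coverage or intraclass correlation (ICC) for these intervals, so there is nothing to reproduce on this point. The SAP Table A powers do reproduce with a two-sample non-inferiority t-test (99.7%, 95.4%, 95.4%; global 1 − 0.095 = 90.5%). They are untouched by this issue.

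**Inputs from the documents.** About 265 participants per arm (SAP 2.5); m = 2 visits (Co-Ad) or 3 visits (Control); m = 3 doses in both arms (SAP Table B).

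**Inputs assumed.** ICC 0.1 to 0.5, and one common event rate across a participant's doses or visits.

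**Formula.** Design effect D = 1 + (m − 1) × ICC. The planned width is about 1/√D of the width it should have, so the shortfall is 1 − 1/√D. Coverage comes from beta-binomial simulation, 20,000 trials per cell, at event rates of 10 to 60%.

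| m | ICC | D | Shortfall in width | Coverage of the planned 95% interval |
|---|---|---|---|---|
| 2 | 0.1 | 1.1 | 5% | 94–95% |
| 2 | 0.3 | 1.3 | 12% | 92–93% |
| 2 | 0.5 | 1.5 | 18% | about 90% |
| 3 | 0.1 | 1.2 | 9% | 93–94% |
| 3 | 0.3 | 1.6 | 21% | about 89% |
| 3 | 0.5 | 2.0 | 29% | 84–85% |

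With ICC 0 the coverage is 95–96%.

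**Example.** Pooled visits, 30% event rate, ICC 0.5. Co-Ad (n = 530): planned width 7.97 points, or 9.81 on the effective sample size of 530/1.5 ≈ 353. Control (n = 795): planned 6.48 points, or 9.24 on 795/2 ≈ 398. As planned, the Control interval is 6.48/7.97 = 0.81 of the Co-Ad width. After adjustment it is 9.24/9.81 = 0.94.

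**Rare events.** At a 1% rate and ICC 0.1, the conservatism of the exact method absorbs the clustering: coverage is about 97% (m = 2) and 95% (m = 3). At ICC 0.5 it is 93.5% and 87.5%.

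**Does it differ by arm?** For pooled visits, yes, at any ICC above 0, because m is 2 in one arm and 3 in the other. For pooled doses, m is 3 in both arms. Let r1 be the correlation between same-day doses and r2 the correlation otherwise. Then D = 1 + (2/3)(r1 + 2 × r2) in Co-Ad and 1 + 2 × r2 in Control.

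- r1 = r2 = 0.3: 1.60 in both arms.
- r1 = 0.7, r2 = 0.3: 1.87 in Co-Ad, 1.60 in Control.
- Same-day doses collapsed to one unit, ICC 0.3: 1.30 in Co-Ad, 1.60 in Control.

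So for dose rows even the direction of any difference depends on a counting rule that the SAP does not give.

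**The case against.** The strongest reply is that little rests on these rows. The protocol's safety endpoints and the SAP 2.4 safety estimands are percentages of participants. The per-dose, per-visit and overall-participant rows have one observation per person, so Clopper-Pearson suits them. SAP 12 and 13 concern concomitant vaccination and medication, which are not endpoints. All of this stands, and it limits the consequence to descriptive pooled rows.

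Second, the pooled denominators in SAP 16.1.1 are inferred. SAP 8 leaves table format and content to templates that are not among the documents reviewed, and these may define them. This also stands. It makes defining the denominator the first step of the remedy, but does not help SAP 12 and 13, where doses are named.

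Third, the size rests on an assumed ICC and on equal rates across doses. The two vaccines differ, and unequal rates reduce the effect. With assumed rates of 70%, 40% and 70% and pairwise correlation 0.3, the variance per participant is 0.66 + 2 × 0.198 ≈ 1.055, against 3 × 0.6 × 0.4 = 0.72 for the pooled binomial. D is then about 1.47 rather than 1.60. The figures above are upper-side estimates where rates differ by vaccine.

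A reader might infer more: that all the safety intervals are too narrow, that every pooled row misleads by a different amount in each arm, or that the reactogenicity objective is compromised. The documents do not support this. Both arms receive three doses, so the arm difference is established only for pooled visits, and the endpoint rows are sound.

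**Conclusion.** The point holds in a limited form and is minor. Followed as written, SAP 6.5 puts independent-binomial intervals on the dose rows of SAP 12 and 13 and, very probably, on the pooled dose and visit rows of SAP 16.1.1. These intervals are too narrow whenever within-participant correlation is positive.

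Under the assumptions listed in the check, the worst case considered is three units per participant at ICC 0.5. There the width falls short by nearly a third and coverage is about ten points below nominal. At ICC 0.1 the loss of coverage is at most about two points, and for rare events with a small ICC it disappears.

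No hypothesis test, sample-size figure or protocol-defined endpoint changes.

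**What to change.** Three changes to the SAP text:

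1. In SAP 6.5, limit Clopper-Pearson to rows with one observation per participant.
2. In SAP 12, 13 and 16.1.1, define the denominators of the pooled dose and visit rows. State how same-day Co-Ad injections count, and whether the count-once rule of SAP 16.1 applies to the denominator as well as the numerator.
3. For the pooled rows, choose one of two options. Either print the percentage without an interval and rely on the overall-participant row, or use a participant-clustered interval (Clopper-Pearson on the effective sample size, or a bootstrap that resamples participants).

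The cost is a few sentences and a change to one table macro, with no new data. The downside is that intervals on some descriptive rows become somewhat wider or are omitted.

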### **16.1.2. Endpoint Level Compliance**

The study protocol defines a 7-day solicited AE follow-up period.

In terms of compliance for each of Days 1-7, the number/percentage of completed eDiaries will be summarized by study group and by visit, using a frequency table. The denominator for each day will be the number of expected completed eDiaries (i.e., the number of participants).

For compliance of each day beyond Day 7, and for each solicited symptom, the number/percentage of completed eDiaries will be summarized by study group and by dose, using a frequency table. In this summary, the denominator for each symptom will be the number of expected completed diaries (i.e., the number of participants with the symptom on previous days) and the numerator will be the number of participants with eDiaries completed among the participants contributing to the denominator.

### **16.1.3. Unsolicited Adverse Events**

All unsolicited adverse events summaries will be reported by MedDRA SOC, HLT, PT.

The verbatim reports of unsolicited AEs will be reviewed by a physician and the signs and symptoms will be coded according to the MedDRA Dictionary for Adverse Reaction Terminology. Every verbatim term will be matched with the appropriate Preferred Term.

Unsolicited events will be summarized and listed as:

- The number and percentage of participants, with exact 95% CIs, with any unsolicited AEs during the 30-day follow-up period (i.e., the day of vaccination [per vaccination type, RSVPreF3 OA, or HZ/su] and 29 subsequent days) will be tabulated following each dose and overall. This summary will be repeated by age group.
  - This summary will be repeated for:

CCI

- Grade 3 unsolicited AEs
- Grade 3 non-serious unsolicited AEs
- Causally related unsolicited AEs
- Causally related, Grade 3 unsolicited AEs
- Unsolicited AEs resulting in a medically attended visit

The above analysis by visit will also be performed.

- The number and percentage of participants, with exact 95% CIs, with any non-serious unsolicited AEs during the 30-day follow-up period (i.e., the day of vaccination and 29 subsequent days) will be tabulated by group and by MedDRA SOC, HLT and PT, following each visit.
  - This summary will be repeated for:
    - Grade 3 non-serious AEs (this summary will be repeated by age group)
    - Causally related non-serious unsolicited AEs
    - Causally related, Grade 3 non-serious unsolicited AEs
    - Non-serious unsolicited AEs resulting in a medically attended visit
- The number and percentage of participants, with exact 95% CIs, with any unsolicited AEs with onset within 30 minutes of any dose will be tabulated by group and by MedDRA SOC, HLT and PT, following each dose. This summary will be repeated for Grade 3 unsolicited AEs.
- Subgroup analysis will be created for the unsolicited events and grade 3 unsolicited events within 30 days of each dose split by age category, race, ethnicity and gender.

All the summaries for unsolicited AEs during the 30-day follow-up period and non-serious unsolicited AEs during the 30-day follow-up period will be repeated by visit.

[figure not shown]
All unsolicited AEs will be included in a listing. All solicited (administration site and/or systemic AEs) and unsolicited AEs leading to study discontinuation or vaccine discontinuation will be included in a listing.

All atrial fibrillation events will be included in a listing.

#### **16.1.4.     Solicited and Unsolicited Adverse Events**

- For clinicaltrials.gov and EudraCT posting purposes, the following summary will be produced :For web

CCI

posting purposes, the number of occurrences and the number and percentage of participants with non-serious AEs (solicited and unsolicited combined) during the 30-day follow-up period of any dose will be produced by SOC and PT.

### **16.1.5. Serious Adverse Events**

Analysis of serious adverse events (SAEs) from first vaccination (Visit 1, Day 1) up to 6 months post-last vaccination, the reporting period will start at vaccination and will end at approximately 6 months post-last vaccination (i.e., day of last vaccination+[180-210]).

SAEs will be summarized and listed as:

[figure not shown]
- The number and percentage of participants, with exact 95% CIs, with at least one report of SAE with onset after each vaccine administration up to study end (i.e. 6 months post-last vaccination). This summary will be repeated for:
  - Causally related SAEs
  - Fatal SAEs
- All SAEs will be included in a listing.
- All SAEs leading to study discontinuation or vaccine discontinuation at any point from first vaccination up to study end will be included in a listing and a tabulated listing.
- For web posting purposes, the number of occurrences and the number and percentage of participants with at least one SAE with onset after each vaccine administration up to study end (i.e. 6 months post-last vaccination) will be produced by SOC and PT. The same table will be produced for related SAE, fatal SAE and related fatal SAE.

Subgroup analysis will be created for the serious events up to study end (6 months after last dose) split by age category, race, ethnicity and gender.

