To evaluate the humoral immune response to RSVPreF3 OA investigational vaccine when co-administered with the first dose of HZ/su vaccine or administered alone.	
 
RSV-A neutralizing titers expressed as GMT at pre-vaccination and at 1-month after the RSVPreF3 OA investigational vaccine dose.
 
RSV-A neutralizing titers expressed as MGI at 1-month after the RSVPreF3 OA investigational vaccine dose.
 
RSV-B neutralizing titers expressed as GMT at pre-vaccination and at 1-month after the RSVPreF3 OA investigational vaccine dose.
 
RSV-B neutralizing titers expressed as MGI at 1-month after the RSVPreF3 OA investigational vaccine dose.
 

To evaluate the safety and reactogenicity following administration of the RSVPreF3 OA investigational	
 
Percentage of participants reporting each solicited administration site and systemic
 

Objectives	Endpoints
vaccine and the HZ/su vaccine, co-administered or administered alone.	
event with onset within 7 days after vaccine administration (i.e., the day of vaccination and 6 subsequent days).
 
 
Percentage of participants reporting unsolicited AEs with onset within 30 days after vaccine administration (i.e., the day of vaccination and 29 subsequent days).
 
Percentage of participants reporting all SAEs after vaccine administration (Day 1) up to study end (6 months after last vaccination).
 
Percentage of participants reporting all pIMDs after vaccine administration (Day 1) up to study end (6 months after last vaccination).
 

Abbreviations: AE=adverse event; CI=confidence interval; gE=glycoprotein E; GMC=geometric mean concentration; GMT=geometric mean titer; HZ/su=herpes zoster recombinant subunit; MGI=mean geometric increase; OA=older adult; pIMD=potential immune-mediated disease; RSV=respiratory syncytial virus; SAE=serious adverse event.

\* Zoster and RSV-A related endpoints will be assessed as co-primary. RSV-B related endpoints will be assessed as sequential to the success of Zoster and RSV-A.

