Secondary	RSVPreF3 OA (one dose) and HZ/su (two doses) co-administered (Co-Ad) or received separately (Control)	Adults aged $\geq$ 50 YOA	Each Potential Immune-Medicated Disease (pIMD) event up to study end (6 months after last vaccination)	1. Permanently discontinued from study due to any reasons prior to end of study	1. Missing data won't be imputed. Summaries will present the actual data	Percentage and exact 95% CIs of participants with all pIMDs up to study end (Days 1-183 after each vaccine [i.e., date of RSVPreF3 OA vaccine administration for Control group becomes Day 1 for recording events within 6 months])

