### 3. STUDY DESIGN

#### 3.1. General Description

This is a phase III, open-label, randomized, controlled, multi-country study in medically stable older adults of  $\geq 50$  YOA with two parallel groups. Participants will be randomly assigned to 2 study groups at Visit 1 (Day 1):

- Co-administration (Co-Ad) group: Study interventions will be administered on Visit 1 (Day 1) in which participants will receive both HZ/su vaccine and RSVPreF3 OA investigational vaccine; and on Visit 3 (Day 61) in which the second dose of HZ/su vaccine will be administered. A total of four site visits (Visit 1 [Day 1], Visit 2 [Day 31], Visit 3 [Day 61] and Visit 4 [Day 91]) and a remote contact 6 months post-last vaccination are needed.
- Control group: Study interventions will be administered on Visit 1 (Day 1) in which participants will receive HZ/su vaccine, Visit 2 (Day 31) in which participants will receive RSVPreF3 OA investigational vaccine; and Visit 3 (Day 61) in which participants will receive the second dose of HZ/su vaccine. A total of four site visits (Visit 1 [Day 1], Visit 2 [Day 31], Visit 3 [Day 61] and Visit 4 [Day 91]) and a remote contact 6 months post-last vaccination are needed.

CCI

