### **16.1.6. pIMDs**

For analysis of pIMDs, the reporting period will start at vaccination and will end at approximately 6 months post-last vaccination (i.e., day of last vaccination+[180-210]. pIMDs will be summarized by MedDRA SOC, HLT and PT. pIMDs will be summarized and listed as follows:

CCI

- The number and percentage of participants, with exact 95% CIs, with at least one report of pIMD (all pIMDs, causally related separately) with onset after each vaccine administration up to study end (i.e. 6 months post-last vaccination) will be summarized.
- All pIMDs will also be described in detail in a listing and a tabulated listing of pIMDs leading to discontinuation of study will be provided. Classification by new onset vs exacerbations of pIMDs will also be presented.
- The number and percentage of participants, with exact 95% CIs, with at least one report of neurological demyelinating pIMD with onset within 30 days of any dose will be summarized. This summary will be repeated for serious neurological demyelinating pIMDs with onset after each vaccine administration up to study end.
- Subgroup analysis will be created for the serious events up to study end (6 months after last dose) split by age category, race, ethnicity and gender.

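### The SAP gives conflicting counting windows for SAEs and pIMDs; one of them, if programmed per vaccine, follows RSV 30 planned days longer in Co-Ad than in Control

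*SAP*

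**What the plan says.** Protocol Table 6 states the SAE endpoint as "Percentage of participants reporting all SAEs after vaccine administration (Day 1) up to study end (6 months after last vaccination"; the pIMD endpoint has the same start and stop. The SAP's list of secondary safety endpoints (section 16) carries both over with that period.

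SAP 16.1.5 opens in line with this: "Analysis of serious adverse events (SAEs) from first vaccination (Visit 1, Day 1) up to 6 months post-last vaccination". The reporting period closes at "approximately 6 months post-last vaccination (i.e., day of last vaccination+[180-210", that is, 180 to 210 days after the last dose. The main summary bullet in the same section then counts participants "with at least one report of SAE with onset after each vaccine administration up to study end". The SAE table for web posting repeats that rule. SAP 16.1.6 applies it to pIMDs: "with onset after each vaccine administration up to study end (i.e. 6 months post-last vaccination) will be summarized".

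The SAE and pIMD rows of the estimand table (SAP 2.4) give a third version, a fixed window of Days 1-183 after each vaccine, in which the "date of RSVPreF3 OA vaccine administration for Control group becomes Day 1 for recording events within 6 months". Both rows also say that counting runs to study end, and the SAE row adds that it starts after the last dose of study intervention.

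On dosing, SAP 3.1 says for Co-Ad: "Study interventions will be administered on Visit 1 (Day 1) in which participants will receive both HZ/su vaccine and RSVPreF3 OA investigational vaccine". For Control it says: "Visit 2 (Day 31) in which participants will receive RSVPreF3 OA investigational vaccine". Both groups receive the second HZ/su dose at Day 61.

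**The concern.** A programmer cannot satisfy all of these texts. Take an SAE on Day 20. It counts from Day 1 to study end, but not if counting starts after the last dose on Day 61. Take an SAE on Day 220. It counts from Day 1 to study end, but it falls outside the Days 1-183 window after RSV in both groups.

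The choice also affects fairness between groups. Study end is tied to the second HZ/su dose, whereas RSV is given at different times in the two groups. A window that opens at the RSV dose and closes at study end is therefore longer in Co-Ad. Comparing co-administered with separate vaccination is a stated safety objective, and percentages with exact confidence intervals will be read side by side. A longer window in one group raises its percentage even when the underlying risk is the same.

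**Working it through.** **Inputs.** RSV dose: Day 1 (Co-Ad), Day 31 (Control). Second HZ/su dose: Day 61 in both (SAP 3.1). Planned intervals, with allowed ranges, from Protocol Tables 3-4 and SAP Tables C-D:
- Visit 1 to Visit 3 in Co-Ad: 60 days (60-84).
- Visit 1 to Visit 2, and Visit 2 to Visit 3, in Control: 30 days each (30-42).
- Visit 3 to the final contact: 180 days (180-210).

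**The plan's own figure.** SAP 3.1 puts the safety contact on Day 243. Counted inclusively from the last dose, 243 − 61 + 1 = 183, which matches the Days 1-183 of SAP 2.4. The interval tables give 61 + 180 = Day 241, two days earlier. So Days 1-183 reaches study end only for the last dose. For RSV it ends on Day 183 in Co-Ad and on Day 31 + 182 = Day 213 in Control. Within the 2.4 rows, a 183-day window after each vaccine and counting to study end are therefore different rules.

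**Planned follow-up under each definition.**

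| Definition | Co-Ad | Control |
|---|---|---|
| First vaccination to study end | 60 + 180 = 240 | 30 + 30 + 180 = 240 |
| Fixed window after RSV (SAP 2.4) | 183 | 183 |
| RSV dose to study end (16.1.5-16.1.6 read per vaccine) | 60 + 180 = 240 | 30 + 180 = 210 |
| HZ/su dose 1 to study end | 240 | 240 |
| HZ/su dose 2 to study end | 180 | 180 |

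Only the RSV-to-study-end line differs between groups: 240/210 = 1.14. Its allowed ranges are 60 + 180 = 240 to 84 + 210 = 294 days in Co-Ad, and 30 + 180 = 210 to 42 + 210 = 252 in Control. Using Day 243 instead gives 242 and 212 elapsed days, the same 30-day gap.

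**Effect on the percentages.** The documents give no SAE or pIMD rate, so the risk p over 240 days is an assumption. With a constant hazard, the 210-day risk is 1 − (1 − p)^(210/240):

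| Assumed p (Co-Ad, 240 days) | Control, 210 days | Gap, percentage points | Expected participants per 265 |
|---|---|---|---|
| 2% | 1.75% | 0.25 | 5.3 vs 4.6 |
| 4% | 3.51% | 0.49 | 10.6 vs 9.3 |
| 6% | 5.27% | 0.73 | 15.9 vs 14.0 |

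**Which fixed window is fully observed.** A 183-day window after the second HZ/su dose ends on Day 243, but with that dose on Day 61 the contact may take place on Day 241. A 180-day window is complete for every participant contacted within the allowed interval.

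**The case against.** The strongest reply is that the unequal row may not exist. SAP 16.1.5 and 16.1.6 do not define rows per vaccine or per dose. For solicited and unsolicited events the SAP asks explicitly for results by dose and overall; here it does not. Given the opening sentence of 16.1.5, the bullet can be read as any onset after vaccination. This stands, in that a separate RSV row is a reading and not a stated fact. It is still a plausible reading. The SAP says any dose when it means that, including in the neurological demyelinating bullet of 16.1.6, which separates that wording from each vaccine administration. SAP 6.1 ties the reference date to the first dose of each study vaccination, and 2.4 restarts the clock at the Control RSV dose.

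A reader might also infer that the SAP plans no fixed window, or that it has dropped the protocol endpoint. Neither is supported. SAP 2.4 states a fixed 183-day window, under which the clock reset makes RSV follow-up equal. Section 16 keeps the Day 1 to study end endpoint. The problem is that these texts stand beside a different rule.

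A reader might further infer that the shorter window after the second HZ/su dose biases the group comparison. It does not: 240 and 180 days apply in both groups, and comparing dose 1 with dose 2 is not an objective.

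Finally, the SAP plans no statistical comparison of groups for safety, SAEs and pIMDs are listed in full, and the possible distortion is one or two participants per group. All of this stands and limits the weight of the point.

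**Conclusion.** The SAP contains conflicting SAE and pIMD windows, and this holds whatever the table shells show. One of them, if programmed as rows per vaccine, gives RSV 240 planned days in Co-Ad against 210 in Control. At equal and constant hazard, Co-Ad would then read about 14% higher in relative terms, or about 0.25 to 0.7 percentage points for an assumed 2-6% risk over 240 days. The direction is always against Co-Ad.

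The documents do not support saying that the reported RSV percentages will differ by construction. That depends on an unseen layout, and two of the SAP's own definitions give equal windows. The overall Day 1 to study end percentage is unaffected, as are the primary immunogenicity conclusions. This is a matter of clear specification and fair descriptive display, and it should be corrected.

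**What to change.** Reconcile SAP 2.4 with section 16, 16.1.5 and 16.1.6:

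- Make the SAE and pIMD endpoint tables, including the SAE web-posting tables, one row per participant from first vaccination to study end, as in Protocol Table 6.
- Remove the reference to the period after the last dose from the SAE estimand row.
- For any per-vaccine row, replace the open end at study end with one fixed window of equal length in both groups, and state it identically in 2.4, 16.1.5 and 16.1.6. A window of 180 days is preferable to 183 because it never runs past the earliest permitted contact.
- Footnote that per-vaccine windows overlap, so one event can appear under more than one vaccine.

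The cost is SAP wording and a window flag in programming; no new data are needed. The small downside is that events after the fixed window appear only in the overall row.
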